single use of cannabis is typically 3-4 days (based on a 50 ng/mL cutoff level) or up to 7 days (based on a 20 ng/mL cutoff for cannabinoids) using urinalysis (Huestis, Mitchell, & Cone, 1996). Thus most previous CM approaches for CUD require clinic-based monitoring at least twice a week to verify abstinence. Clinic-based urine testing is burdensome, as participants must travel to attend clinic sessions.

In contrast to traditional urine- or blood-based drug testing approaches, saliva (oral fluid, or OF) testing is a relatively new form of drug testing. OF testing is non-invasive and has the benefits of directly observable sample collection methods (reducing potential for sample adulteration), lower biohazard risk during collection, ease of multiple sample collections, and stronger correlation with blood than urine concentrations (Lee & Huestis, 2014). In contrast to urinalysis, which detects cannabis metabolites, the majority of current OF devices directly measure $\Delta 9$ -tetrahydrocannabinol (THC). The reliability and validity of OF drug testing has improved significantly over the past decade (Lee & Huestis, 2014). There is currently an FDA-approved saliva testing method (Oratect® AOT-06 Oral Fluid Drug Screen Device) that can be used to detect THC use (40 ng/mL) in the past 6-12 hours. To date, no studies have examined the feasibility of using OF testing methods for CM to treat CUD.

The use of OF testing methods would eliminate the need for a long washout period before abstinence could be reinforced *via* CM. We expect that the combination of CO monitoring and saliva testing can significantly increase the feasibility of CM for CUD. We expect that verification of abstinence without the necessity of clinic visits is possible using mobile technology, expired CO and saliva testing. We will examine the feasibility of using both random saliva screens (assessing cannabis use in last 6-12 hours) administered at high risk use times and CO (assessing smoked cannabis use in the last 3 hours).

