application (mCM) targeting BOTH smoking and cannabis use. Treatment components are separately described herein. Table 1 provides a summary of study visits, procedures, and compensation.

Table 1. Stu	Table 1. Study Procedures						
Session	Tasks	Time	Payment				
1 (lab)	Consent	30 min	\$100				
	Screening (clinical interview, questionnaires,	3 ½ hours					
	impulsivity tasks)						
	Urine sample, breath sample taken						
	Counseling session 1						
	mCM equipment training						
2 (phone)	Counseling session 2	30 mins.	None				
3 (phone)	Counseling session 3	30 mins.	Up to \$49 for monitoring				
	Begin practice mCM for 1 week		between 3 & 4				
	Begin bupropion if using						
4 (phone)	Quit day	30 mins.	Up to \$402.50 for 2 weeks				
	Counseling session 4		monitoring between 4 & 5				
	Begin abstinence mCM						
	Begin NRT						
5 (phone;	Counseling session 5	30 mins.	Up to \$892.50 for 2 weeks				
2 wks post	Continue abstinence mCM		monitoring between 5 & 6				
session 4)	Reduce NRT to 14 mg						
	Continue use of "rescue" NRT PRN						
6 (phone;	Quick phone check-in	10 min	Up to \$98 for monitoring				
2 wks post	Continue mCM wash-out period		between 6 & 7				
session 5)	Reduce NRT to 7 mg						
	Continue use of "rescue" NRT PRN						
7 (lab; 2	Feasibility interview, question naires,	1 hour	\$35 for returned				
wks post	impulsivity tasks		equipment, \$100 for				
session 6)	Saliva sample, CO reading, and urine drug		session				
	screen Prompt to return equipment						
	Cease NRT						
8 (lab; 3	Questionnaires, impulsivity tasks	30 min	\$100				
month	Saliva samples, CO readings, and urine drug						
follow-up)	screens						
9 (lab; 6	Questionnaires, impulsivity tasks	30 min	\$100				
month	 Saliva samples, CO readings, and urine drug 						
follow-up)	screens						
	Cease bupropion						
		TOTAL	Up to \$1,877				

Measures. At the screening visit, participants will provide sociodemographic data on age, gender, education, income, ethnicity, marital and employment status. They will be interviewed using the substance use disorders section and the psychotic and associated symptoms section of the Structured Clinical Interview for DSM-5 (SCID-5; First, Williams, Karg, & Spitzer, 2015). Participants will also

complete the following measures:

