mCM Procedures. As part of previous projects (see Duke PRO00031703, PRO00050835, PRO61683, and PRO00062101), we developed a smart phone app that allows CM to be used outside the clinic to address substance misuse. Our programmer has completed adaptation of our existing mCM application to integrate the assessment of cannabis abstinence into the design of the app. Though most of the procedures used in our previous mCM studies are easily applied to CUD, we have made several important changes. We have added a videotaped OF assessment in which participants record themselves self-administering a OF test kit. For each OF video recording, each participant will be asked to 1) begin a recording using the smartphone device; 2) show the unused test strip to the camera; 3) swab his or her cheek while on camera; and 4) place the strip on a flat surface for 5 minutes and 5) show the final result to the camera. Saliva sticks will be numbered so that the number associated with the saliva swab can be ensured to be the number of the swab result. Participants will provide a CO reading and THC OF reading twice daily. Because reinforcers are most effective when delivered immediately after the target behavior is performed (Lattal, 2010), the phone app provides daily feedback on abstinence status, financial amount earned, and how the amount was calculated.

Video recordings will be made using a DROID MAXX 2 with an octa-core 1.7 Ghz processor, 2 GB RAM, and 5.5" full HD display. The operating system (OS) being utilized for the smart phones is Android 5.1.1 Lollipop, see FIPS 140-2 certificate 1998. The CO breath monitor, the iCO Smokerlyzer, is a battery

operated instrument that measures CO in ppm

(http://www.bedfont.com/shop/smokerlyzer/ico_smokerlyzer). The Bedfont/coVita iCO™ Smokerlyzer® plugs into a smart phone by means of the headphone jack, and communicates with the smart phone app developed by our team. Participants are able to see the CO reading within the app, and the app collects the CO data directly. Data are stored in the same manner as the videorecordings that participants upload (see below and in "Protection From Risks: Data Security" herein).

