With regards to FDA device issues, Bedfont/coVita will not be seeking 510k Clearance on the iCO™ Smokerlyzer® because it does not meet the standard/criteria of a medical device. Device manufacturers are required to follow FDA guidance to inform them of when a device necessitates 510k application. Per [name] at Bedfont/coVita, their regulatory team has determined that this is not necessary primarily because they do not make a medical claim about the device, as it is not designed to diagnose a disease or illness. Simply measuring CO is not diagnosing a disease or illness and Bedfont/coVita makes no medical claim that the iCO™ Smokerlyer® can be used to screen for CO poisoning.

We will compare self-reports to objective measures of cannabis use during the abstinence period. Feasibility of using proposed methods will be based on the observed concordance of self-report, CO readings, and saliva testing in the early abstinence period. If saliva tests taken before bedtime do not coordinate with participants' self-report during early abstinence weeks 1-2, we will modify procedures for subsequent weeks in order to 1) increase frequency of monitoring and 2) have the timing less predictable; e.g., more frequent cannabis readings will occur randomly between 8am-11pm, clustered in the evenings (8pm-11pm) and weekends (Friday-Sunday) (Alessi & Petry, 2013). While potentially more burdensome, this modification will be designed to alarm-prompt readings to occur up to 14 occasions each week to ensure adequate coverage. This procedure is designed to ensure that participants do not know when they will have a long time period between readings that would provide an opportunity for using cannabis that would be metabolized before the next reading. When prompted, participants will have one hour to submit their sample, with a reminder prompt at 30 minutes. Similar procedures have produced good adherence in previous research (Alessi & Petry, 2013). At the end of the monitoring period, qualitative data will be collected assessing bio-verification preferences, barriers, and any attempts to tamper or alter samples.

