Participants will receive training on mCM procedures, including use of the mCM app, CO monitor, and saliva kits, by study staff. If equipment is available for loan at the screening visit, participants will be given smartphones with the mCM app, a CO monitor, and numbered saliva kits. If equipment is not immediately available for loan, these things will be mailed to the study participant prior to his/her beginning the mCM monitoring phase of the study. After one week with no mCM activity, they will complete one week of baseline saliva assessments and CO monitoring to ensure that they are expert at using the mHealth technology and can troubleshoot any problems with the assistance of study staff. During the baseline week, participants will be reinforced for completing readings, regardless of abstinence. The baseline monitoring will be followed by four weeks of active mCM. Because an escalating, versus a fixed, reinforcement schedule has produced higher abstinence rates (Heil et al., 2008; Stoops et al., 2009), an escalating schedule will be used in this protocol (identical to our pilot studies). Participants will provide substance use data throughout the mCM phase simply by completing

their readings using the mCM app. After the practice week, monetary reinforcement will be contingent on abstinence from marijuana and tobacco smoking, operationally defined as THC readings that are < 40 ng/mL and CO readings that are < 6 ppm. Following the active CM treatment phase, two weeks of saliva tests and CO monitoring (without contingent reinforcement) will be completed so that we can assess the durability of treatment effects.

During the entire monitoring period, each evening, participants will answer a computerized daily diary (programmed by our mCM app developer) in which they'll be asked to report on cigarette smoking and cannabis use. Participants will be asked 1) if they smoked cigarettes; 2) how many cigarettes they smoked if applicable; 3) if they smoked marijuana and how many if applicable; 4) if they ingested marijuana and how much; and 5) if they vaped marijuana and how much. Participants will be paid \$1 per day for completing the diary.

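### Feasibility of home saliva monitoring rests on agreement with self-report and CO, so use that is missed and denied counts as agreement; the session-7 urine could offer a partial check but is not compared with the home record

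*Combined protocol and SAP*

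**What the plan says.** All references are to the combined protocol and SAP.

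- **Criterion (Methods, mCM Procedures).** "Feasibility of using proposed methods will be based on the observed concordance of self-report, CO readings, and saliva testing in the early abstinence period". No agreement threshold is given.
- **Trigger (same section).** Monitoring is changed "If saliva tests taken before bedtime do not coordinate with participants' self-report during early abstinence weeks 1-2". CO is not part of this trigger.
- **Schedule.** "Participants will provide a CO reading and THC OF reading twice daily". After four weeks of abstinence-contingent pay, "two weeks of saliva tests and CO monitoring (without contingent reinforcement) will be completed". An evening diary of cannabis and cigarette use runs throughout the monitoring period.
- **Session 7 (Table 1).** The lab visit two weeks after session 6 lists "Saliva sample, CO reading, and urine drug" screen. Follow-Up Visits uses urine and oral fluid to verify self-reported prolonged abstinence, with a 50 ng/ml cut-point for THC-COOH.
- **Data Analyses.** The utility of the saliva protocol will be examined, with no comparator or metric named. Qualitative data cover acceptability, and mCM Procedures adds a question on tampering.

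No section compares urine with the home saliva readings.

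**The concern.** Concordance shows whether the sources agree, not whether they detect use. If a participant uses cannabis outside the window of the next saliva test and does not report it, saliva and diary are both negative and the day scores as agreement. CO adds little: by the Background it looks back 3 hours, responds only to smoked cannabis, and is also raised by tobacco. The tampering question relies on self-report again.

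The protocol recognises the risk. It gives the purpose of less predictable timing as preventing use that would clear before the next reading. Yet that change starts only if saliva and self-report disagree, which missed and denied use does not produce.

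The stake is the conclusion about the bioverification method, one of the three feasibility aims (with treatment and recruitment) meant to support a larger grant. High concordance could carry the saliva protocol forward although it misses use.

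**Working it through.** The plan states no figure on this point, so there is none to reproduce.

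**1. Agreement and detection.** Let p be the share of days with use, s the sensitivity of the saliva protocol, and d the share of missed use that is denied. Assume specificity 1 and that detected use is admitted. Then agreement between saliva and self-report = (1 - p) + p·s + p·(1 - s)·d. The documents give none of these inputs, so a range is shown:

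| p | s | d = 0 | d = 0.5 | d = 0.9 | d = 1 |
|---|---|---|---|---|---|
| 0.1 | 0.25 | 92.5% | 96.25% | 99.25% | 100% |
| 0.1 | 0.50 | 95% | 97.5% | 99.5% | 100% |
| 0.3 | 0.25 | 77.5% | 88.75% | 97.75% | 100% |
| 0.3 | 0.50 | 85% | 92.5% | 98.5% | 100% |
| 0.5 | 0.25 | 62.5% | 81.25% | 96.25% | 100% |
| 0.5 | 0.50 | 75% | 87.5% | 97.5% | 100% |

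With full denial, agreement is 100% whatever the sensitivity.

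**2. Can use fall between readings?** The Background gives saliva a 6-12 h window. Two readings a day cover at most 2 × 6 = 12 h to 2 × 12 = 24 h of 24. With readings at 08:00 and 23:00 (assumed times), 12 h are uncovered at a 6 h window and 3 h at a 12 h window.

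**3. What session-7 urine can reach.** From Table 1, session 7 falls on day 14 + 14 + 14 = 42 after quit; days 1-28 carry abstinence-contingent pay. The Background gives urine a single-use window, after washout, of 3-4 days at 50 ng/mL and up to 7 days at 20 ng/mL.

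| Look-back | Share of 42 days | Share of last 14 days | Days reached in weeks 1-2 | Days reached of the 28 |
|---|---|---|---|---|
| 3 days | 7% | 21% | 0 | 0 |
| 4 days | 10% | 29% | 0 | 0 |
| 7 days | 17% | 50% | 0 | 0 |
| 14 days (carry-over) | 33% | 100% | 0 | 0 |

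The Background puts washout in regular users at 1-2 weeks or longer. Carry-over beyond 14 days could reach the contingent phase, but such a positive is ambiguous.

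**4. Urine against the saliva series.** In the last 4 days there are 4 × 2 = 8 scheduled saliva readings, covering at most 8 × 6 = 48 h to 8 × 12 = 96 h if windows do not overlap. One urine sample covers 3 × 24 = 72 h to 4 × 24 = 96 h.

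**5. Precision.** The plan enrols up to 10 and aims for 5 completers. If a share q of participants has missed and denied use inside the urine window (assumed), and urine detects it, the chance of flagging at least one is 1 - (1 - q)^n:

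| n | q = 0.1 | q = 0.2 | q = 0.3 | q = 0.5 |
|---|---|---|---|---|
| 5 | 0.41 | 0.67 | 0.83 | 0.97 |
| 10 | 0.65 | 0.89 | 0.97 | 0.999 |

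If none is flagged, the upper limit of the exact two-sided 95% interval is 1 - 0.025^(1/n): 52% for n = 5 and 31% for n = 10.

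**The case against.** The strongest objection is that the remedy does not reach the period criticised. Concordance is judged in early abstinence, and step 3 shows that for single use the session-7 urine covers none of weeks 1-2 and none of the contingent phase. This stands. A reader might infer that the scheduled urine could expose missed use in the weeks where feasibility is decided; the schedule does not support that.

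Other stronger readings also fail:

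- **Urine looks back 6-16 times further than saliva.** That is 72-96 h divided by 6-12 h, one sample against one. Against the 8 scheduled readings the ratio is 72/96 = 0.75 to 96/48 = 2. The 6-16 figure should not be used.
- **Participants can anticipate the readings.** The Background calls the saliva screens random, whereas mCM Procedures makes less predictable timing a later modification. This is a conflict to reconcile, not an established fact.
- **Pay rewards denial.** Abstinence pay depends on THC and CO readings; the diary earns $1 a day for completion. Under the written rules, admitting missed use in the diary costs nothing.
- **The urine is unused.** It verifies self-reported abstinence at session 7, so a participant who denies all use but tests positive would show up there. That tests the self-report, not the saliva method.

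Carry-over is also a fair objection. Entry requires 40 or more days of use in 90, so a urine positive may reflect earlier use, honestly reported.

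Some points do not remove the gap. The protocol promises to compare self-report with objective measures generally, but its next sentence names the three home sources, and Table 1 lists no urine for the phone sessions. Filmed swabbing and numbered sticks address substitution, not timing. The practice week gives saliva and diary data without abstinence pay, but self-report remains the comparator.

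**Conclusion.** The point holds in a limited form. As written, agreement among the home sources cannot separate a protocol that detects use from one that misses use which is then denied, and missed and denied use does not fire the weeks 1-2 trigger. This follows from the definition of agreement; only the sizes in step 1 rest on assumed p, s and d.

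The documents do not show that the saliva protocol is insensitive or that participants will conceal use. They report excellent device agreement with GC/MS, which concerns the sample tested rather than the hours between samples.

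The session-7 urine is a partial, imprecise check: about 5 pairs, at most 10, mostly informative about the last 3-4 days of a phase without abstinence pay. It is still the only longer-window biological check on the home saliva record available from samples already planned. A flagged participant could change the feasibility conclusion; an absence of flagged participants would be weak reassurance. This is a cheap improvement, not a defect that invalidates the pilot.

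**What to change.** 1. **Add one descriptive table to Data Analyses.** For each participant attending session 7, set urine THC-COOH (50 ng/ml) against any positive home saliva reading or diary-reported use (a) in the last 4 days and (b) in the last 14 days, with the number of missed readings shown.
2. **Classify the unexplained positives in advance.** A urine-positive participant with no home positive and no reported use in the 14 days is possible missed use. List separately as indeterminate (possible carry-over) those with a positive reading or reported use earlier after the quit date. Carry-over from before the quit date cannot be wholly excluded either.
3. **Amend mCM Procedures** to say that concordance will be described but will not alone be taken as evidence that the saliva protocol detects use.
4. **State the limits with the table:** its reach of 3-4 days for single use, the 48-96 h against 72-96 h comparison, the expected 5 pairs, and the 52% (or 31%) upper limit if none is flagged.

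Comparing the in-lab saliva result with the last home result is optional and weak, because the two tests cover different hours.

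The cost is one table and a few sentences, with no new samples. Checking weeks 1-2 or the contingent phase directly would need urine collected then, with early results still subject to washout.

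A related passage to reconcile: the modification is meant to raise frequency, yet "alarm-prompt readings to occur up to 14 occasions each week" equals the existing schedule of 2 × 7 = 14.
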